#### **9.4.3 Analysis of the Secondary Endpoint(s)**

The first secondary endpoint is a binary outcome indicating whether a patient needed a mechanical ventilation. We will compute the proportion of patients who needed mechanical ventilation during their treatment for each matched group. The proportion in HBOT arm will be compared with that in matched SOC using chi-square test for proportions. Estimate of difference in proportion along with 95% confidence interval will be reported. Similar to the primary analysis, we will adjust for any potential confounders, deemed important in the baseline analysis, by using multivariable logistic regression. Estimate of odds-ratio and 95% confidence interval will be reported.

To compare the average number of days spent in ventilator between the two groups, we will use linear regression analysis. The distribution of outcome, the number of days in ventilator, will be assessed graphically and by conducting test for normality. If we find the evidence of deviation from normal distribution the outcome will be log transformed before proceeding with analysis. We will also adjust for any potential confounders, deemed important in the baseline analysis. Slope coefficient along with 95% confidence interval will be reported as an estimate of difference between HBOT and SOC groups.

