## 2 Introduction, Background Information and Scientific Rationale

### 2.1 *Background Information and Relevant Literature*

A novel coronavirus, similar to the one that caused severe acute respiratory syndrome (SARS) that began in Wuhan, China, is now a pandemic. With first cases confirmed in the United States nearly 4-6 weeks ago, we anticipate this spread will continue to increase before it plateaus or even decreases. It is highly contagious and is quickly evolving. The first cases were originally linked to animal-human transmission but has since then been transmitted from human-to-human at an exponential rate. Aerosol transmission through respiratory droplets from coughing or sneezing is another primary mechanism.

However, those individuals that are affected have presented in variable clinical presentations from asymptomatic to mild disease to extensive systemic immune reactions requiring mechanical ventilatory assistance. The pathogenic mechanism is still under research but seems complex. The viral infection amounts an excessive immune reaction within the host, activating leukocytes and interleukins that maintain a pro-inflammatory disease state.

Hospital staff, beds, and supplies are limited. The growing number of patients requiring supplemental oxygen and mechanical ventilation is increasing. There is an urgent need to capture this subset of COVID-19 patients prior to clinical respiratory deterioration.

Hyperbaric oxygen therapy (HBOT) presently has been trialed in Wuhan and Italy and has shown feasibility and safety. Hyperbaric oxygen provides patients with 100% inhaled oxygen at an increased atmospheric pressure and has been used as adjuvant therapy to decrease inflammatory states. It has been used in supportive therapy for refractory hypoxia, however, the efficacy of HBOT in treating severe hypoxia in patients with COVID-19 has not been evaluated. Due to the severity of this illness further treatment and studies are needed to begin as soon as possible.

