#### **4.2.2 Secondary Study Endpoints**

The secondary endpoints will be whether a patient needed invasive mechanical ventilation and the number of days on a ventilator for those who did receive ventilation. The rate of patients who needed mechanical ventilation among those who received hyperbaric oxygen will be compared to the rate in a matched cohort of patients that received standard of care and did not get hyperbaric oxygen.

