### 9.2 Statistical Hypotheses

For primary endpoint: we hypothesize that the proportion of patients who died in the HBOT group will be lower than that in the SOC group. We will test the hypothesis against the null of no difference in proportions of incident mortality.

For secondary end points:

1. We hypothesize that the proportion of patient who need mechanical ventilation in the HBOT group will be lower than that in the SOC group. We will test the hypothesis against the null of no difference in proportions between the two groups.
2. We further hypothesize that the patients in the HBOT group will spend on average fewer number of days on a ventilator compared to those in the SOC group. We will test the hypothesis against the null that there is no difference in means between the two groups.

Safety analysis: We hypothesize that the rate of any severe adverse effects will be smaller in the HBOT group compared to the SOC group. We will test the hypothesis against the null of no difference.

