### 9.4 Description of Statistical Methods

#### 9.4.1 General Approach

We will summarize the continuous variables using mean, median, standard deviation and ranges, and the categorical variables using frequency and proportions. Variables will also be summarized graphically. Baseline characteristics of the participants who received HBOT will be compared with that of control patients receiving SOC. If we find any significant difference in the baseline variables between the two matched groups, we will adjust for them as covariates in outcome analysis. T-test or ANOVA will be used for continuous variables whereas chi-squared test will be used for comparison of proportions. All tests will be two tailed at significance level of 0.05. Appropriate transformations (such as log transformation) will be considered for any continuous variable that indicates non-normality. Statistical software R and SAS will be used for the analysis.

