### **9.5 Sample Size**

Using a sample of 160 patients, 40 in HBOT arm and 120 in SOC arm (post matching) we can detect a reduction of 22.5% or higher, against the null of no difference, with 80% power at significance level of 0.05, assuming that the mortality rate in SOC arm is about 80%.

For the secondary analysis, our proposed sample of 160 patients will similarly allow us to detect a difference of 22.5% in need for ventilation between HBOT group and SOC group with 80% power. For comparing the continuous outcome of number of days in ventilation, we have 80% power to detect effect size (cohen's d) of 0.51 with 160 patients.

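### The plan does not say how a patient who dies without being intubated is counted in the ventilation endpoint; if need means receipt, that death scores as a good outcome.

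*Combined protocol and SAP*

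**What the plan says.** Section 4.2.2 sets the secondary endpoints as "whether a patient needed invasive mechanical ventilation and the number of days on a ventilator for those who did receive ventilation". The binary item therefore uses *needed*, and the duration item uses *did receive*. Section 9.2 gives the direction of benefit: "We hypothesize that the proportion of patient who need mechanical ventilation in the HBOT group will be lower than that in the SOC group". Section 9.4.3 describes the binary item as "a binary outcome indicating whether a patient needed a mechanical ventilation". It takes the proportion in each matched group, applies a chi-squared test, and then adjusts by logistic regression. Section 9.5 attaches a power statement to it: "our proposed sample of 160 patients will similarly allow us to detect a difference of 22.5% in need for ventilation".

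In-hospital death is handled separately as the primary endpoint (Section 9.4.2). Neither the Protocol Summary nor Sections 3.2, 4.2.2, 9.2, 9.4.2, 9.4.3, 9.4.7.2 and 9.5 give a coding rule for death before intubation. There is also no composite of ventilation and death, no competing-event method, and no definition of need.

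**The concern.** Death before intubation removes the chance of being ventilated. If the chart reviewer records receipt of ventilation, a patient who dies un-intubated is coded as not ventilated. The denominator is the whole matched group, so that patient counts exactly like one who recovers on oxygen.

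The setting makes the event possible. Section 5.2 excludes intubated patients at entry, and Section 9.3 asks for consistent eligibility in SOC, so everyone starts at risk of it. Section 2.1 notes "Hospital staff, beds, and supplies are limited".

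Unequal rates are also possible. There is no randomisation (9.6.1). HBOT patients come through physician referral and consent (5.4, 5.5), while SOC patients come from charts under a requested waiver (5.7). Matching covers age, gender, comorbidity and disease severity (9.3), but not limits on intubation.

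What is at stake is the meaning of the ventilation result. It has its own hypothesis, test, interval, odds ratio and power statement. A lower proportion could reflect fewer patients deteriorating or more patients dying first, and the planned analysis cannot tell these apart.

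**Working it through.** **Inputs.** 40 HBOT and 120 SOC patients (9.3, 9.5). "All tests will be two tailed at significance level of 0.05" (9.4.1). SOC ventilation about 80% (the sample-size paragraph in 9.4.2). SOC mortality about 80% (9.5). Detectable difference 22.5 points at 80% power (9.5), read as 0.80 against 0.575.

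**The plan's own figure.** Normal approximation with pooled null variance:
- pooled proportion = (40 × 0.575 + 120 × 0.80)/160 = 119/160 = 0.744
- SE under the null = √[0.744 × 0.256 × (1/40 + 1/120)] = 0.0797
- SE under the alternative = √[0.575 × 0.425/40 + 0.80 × 0.20/120] = 0.0863
- power = Φ[(0.225 − 1.96 × 0.0797)/0.0863] = Φ(0.797) = 0.787

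Exact enumeration of the uncorrected chi-squared test gives 0.792. The stated 80% reproduces and is not in dispute.

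**Room for un-intubated deaths under the plan's assumptions.** With 80% mortality and 80% ventilation in SOC, the proportion who die un-intubated lies between max(0, 0.80 − 0.80) = 0 and min(0.80, 1 − 0.80) = 0.20. That is 0 to 24 of 120, so anything from none to all of the SOC patients counted as not ventilated. The margins permit the problem; they do not show that it occurs.

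**Effect of an imbalance.** Assume need means receipt and ventilation-or-death is 80% in both groups. If a fraction *u* die un-intubated, the observed ventilation proportion is 0.80 − *u*. The last column sums the binomial probabilities of all 40 v 120 tables with uncorrected chi-squared above 3.84.

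| Un-intubated deaths, HBOT / SOC | Observed ventilation, HBOT / SOC | P(significant) |
|---|---|---|
| 0% / 0% | 80% / 80% | 5% |
| 7.5% / 0% | 72.5% / 80% | 18% |
| 10% / 0% | 70% / 80% | 27% |
| 15% / 0% | 65% / 80% | 49% |
| 0% / 5% | 80% / 75% | 8% |
| 0% / 10% | 80% / 70% | 21% |
| 0% / 15% | 80% / 65% | 42% |
| 5% / 5% | 75% / 75% | 5% |
| 10% / 10% | 70% / 70% | 5% |

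In the HBOT-excess rows almost every significant result favours HBOT. In the SOC-excess rows almost every one goes against it. If both groups have some un-intubated deaths, a 10-point excess in HBOT gives similar values: 24% for 15% v 5%, and 22% for 20% v 10%.

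**In counts.** Start from 32/40 v 96/120, p = 1.0. If 7 of those 32 HBOT patients die un-intubated instead of being ventilated, the table is 25/40 v 96/120. Then chi-squared = 160 × (25 × 24 − 15 × 96)²/(40 × 120 × 121 × 39) = 4.98, p = 0.026. Conversely, at the planned effect, 23/40 v 96/120 gives p = 0.005. If 3 of the 17 non-ventilated HBOT patients had died, and no non-ventilated SOC patient had, ventilation-or-death is 26/40 v 96/120, p = 0.054.

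**Hidden benefit.** If ventilation-or-death is truly 57.5% v 80%, and 10 per 100 SOC but no HBOT patients die un-intubated, observed ventilation is 57.5% v 70%. The chance of significance falls from 79% to 31%.

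**The case against.** The strongest reply is that the plan nowhere says such a death scores as not ventilated. Sections 4.2.2, 9.2 and 9.4.3 say *needed*, and a patient who died of respiratory failure could be judged to have needed ventilation. This stands: the favourable coding is an inference. The ambiguity is still a defect, because reviewers at 11 sites could code the same death differently.

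Second, a reader might infer that the omission favours HBOT. The documents do not support that. They report no rate in either group. A consent and referral screen could leave treatment-limited patients in SOC, which would work against HBOT. Section 7.9 names mechanical ventilation as the rescue for an HBOT patient in respiratory failure. Section 2.1's remark on supplies is general background and reports no patient refused a ventilator.

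Third, a reader might take 18% to 49% as inflated type I error. It is not. Section 9.2's null is equal proportions needing ventilation, and on the receipt reading those proportions truly differ in these scenarios. The test answers its own question correctly; the difficulty is what the answer means.

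Fourth, every in-hospital death counts against its group in the primary analysis, 9.4.7.2 computes mortality and ventilation together at the interim, and 9.4.10 lists individual data. This makes a hidden effect easier to notice. It does not repair the ventilation estimate, because two marginal proportions do not show how many non-ventilated patients died.

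Finally, at the assumed 80% mortality a composite would overlap heavily with the primary endpoint, and substituting it would displace the ventilation objective in 3.2. That argues for adding it beside ventilation alone, not for replacing the endpoint.

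**Conclusion.** The point holds as a gap in definition. The plan does not state how death before intubation enters the first secondary endpoint. On the likelier reading, need as receipt, it enters as a favourable outcome, and any between-group difference in such deaths moves the ventilation comparison in either direction. Excesses of 5 to 15 per 100 in one group give roughly an 8% to 49% chance of a significant ventilation difference where ventilation-or-death does not differ. Equal rates leave it at about 5%.

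These figures rest on three assumptions: the receipt reading, ventilation-or-death at 80% in both groups, and imbalances chosen to show the range. The documents neither state the coding nor report an imbalance, so they do not show that deaths will be presented as treatment success. The effect is confined to one secondary endpoint of a non-randomised pilot; the mortality analysis and the sample-size figure are unaffected. It is worth correcting because it determines what the ventilation result can support.

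**What to change.** In Sections 4.2.2, 9.2 and 9.4.3:
- define need as receipt of invasive mechanical ventilation during the hospital stay, so that death without intubation has a known code at every site;
- add invasive mechanical ventilation or in-hospital death, analysed with the same chi-squared and logistic methods, and state that a claim of reduced ventilation must also be supported by this composite;
- report ventilation alone and death without ventilation, by group, as its components.

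In Section 9.5, note that the ventilation power sentence applies to ventilation alone. Align the Protocol Summary and Section 3.2.

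No new data or patients are needed, since death and ventilation are both already endpoints, and Section 9.1 leaves the formal SAP still to be written. The costs are a minor protocol amendment with IRB approval (12.2) and a composite that overlaps with the primary endpoint and must be read with its components.

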### 9.3 Analysis Datasets

We will compare study endpoints and safety outcomes between the 40 patients who received HBOT treatment with a matched comparison group of 120 patients who received standard treatment. Matching will be based on age, gender, comorbidity, and disease severity. The eligibility criteria for the SOC group will be consistent with that of the HBOT group.

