#### **9.4.4 Safety Analyses**

To assess severe adverse events (SAEs), we will consider otic barotrauma, myopia, oxygen toxicity seizures and acute pulmonary edema. For each patient we will count the total number of SAEs during hospitalization.

SAEs will be summarized by computing mean and standard deviation for each comparison group. We will further compare mean number of SAEs between HBOT and SOC groups using linear regression. The outcome will be log transformed to account for the potential violation of normality. We will report difference in mean along with 95% confidence interval around the mean.

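### The regressions for ventilator days and SAE counts make no provision for unequal variances at about 1:3 group sizes, so default tests and intervals are miscalibrated if the groups differ materially in spread

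*Combined protocol and SAP*

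**What the plan says.** For ventilator days, Section 9.2 sets the null: "We will test the hypothesis against the null that there is no difference in means between the two groups". Section 9.4.3 gives the method: "To compare the average number of days spent in ventilator between the two groups, we will use linear regression analysis". The slope and its 95% interval are reported. A transformation is conditional: "If we find the evidence of deviation from normal distribution the outcome will be log transformed before proceeding with analysis".

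For safety, Section 9.4.4 says: "We will further compare mean number of SAEs between HBOT and SOC groups using linear regression". Here the log transformation is unconditional, and no rule is given for patients with a count of zero.

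Section 9.4.1 names a t-test or ANOVA for continuous variables without saying whether variances are pooled, and adds: "All tests will be two tailed at significance level of 0.05".

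Section 9.3 sets the comparison as "40 patients who received HBOT treatment with a matched comparison group of 120 patients who received standard treatment". Section 9.5 states for ventilator days: "we have 80% power to detect effect size (cohen's d) of 0.51 with 160 patients". Section 4.2.2, however, defines ventilator days only for patients who were ventilated.

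No section mentions a Welch, robust or other unequal-variance method. The only departure from assumptions that is addressed is non-normality.

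**The concern.** The null in Section 9.2 concerns means only. The default standard error in linear regression, like that of the equal-variance t-test, also assumes one residual variance. With three SOC patients for each HBOT patient, the pooled variance is about three-quarters SOC, while a large part of the uncertainty in the difference comes from the smaller HBOT group. If HBOT outcomes are the more variable, the reported standard error is too small. If they are the less variable, it is too large.

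At stake are the p-value and interval for a secondary endpoint, and the interval for the safety comparison in a study whose stated purpose includes safety. Section 9.1 defers the formal SAP to the end of an unblinded study, so the variance estimator could be chosen after the results are known.

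**Working it through.** **Inputs from the documents.** Two-sided 0.05 (9.4.1). 40 v 120 (9.3, 9.5). If only ventilated patients contribute days (4.2.2), the planning rates give 0.80 × 120 = 96 SOC patients and (0.80 − 0.225) × 40 = 23 HBOT patients (9.4.2, 9.5).

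**Assumed.** HBOT:SOC SD ratios of 0.5 to 2, and Poisson event rates. The documents give neither.

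**1. The plan's own figure.** With one common SD, the noncentrality is 0.51 × √(40 × 120/160) = 0.51 × 5.477 = 2.793. Power is Φ(2.793 − 1.96) = 79.8%, or 79.3% with the noncentral t. The figure of d = 0.51 reproduces. It assumes a common SD and that all 160 patients contribute.

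**2. Standard errors when spreads differ.** With group SDs σ₁ (HBOT) and σ₂ (SOC):

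- Pooled: SE² = {[(n₁−1)σ₁² + (n₂−1)σ₂²]/(n₁+n₂−2)} × (1/n₁ + 1/n₂)
- True: SE² = σ₁²/n₁ + σ₂²/n₂
- With q = pooled SE/true SE, the size of the test is about 2[1 − Φ(1.96q)].

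At 40 v 120, taking σ₂ = 1:

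- σ₁ = 2: pooled SE² = (39×4 + 119)/158 × 1/30 = 0.0580; true SE² = 4/40 + 1/120 = 0.1083; q = 0.73; size 15%.
- σ₁ = 0.5: pooled SE² = (39×0.25 + 119)/158 × 1/30 = 0.0272; true SE² = 0.25/40 + 1/120 = 0.0146; q = 1.37; size 0.8%.

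Simulation with normal outcomes and equal means agrees with these values. The formula gives 3.9% and 6.2% at ratios 0.9 and 1.1.

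| HBOT:SOC SD ratio | 40 v 120, default | 23 v 96, default | HC3, both |
|---|---|---|---|
| 0.5 | 0.8% | 0.5% | about 5% |
| 1.0 | about 5% | about 5% | about 5% |
| 1.5 | 10.7% | 12.3% | 5.0-5.4% |
| 2.0 | about 15% | about 18% | 5.0-5.5% |

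At 40 v 40 the two standard errors coincide and size stays at about 5%, so the unequal group sizes drive the problem.

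**3. Does the planned log transformation cure ventilator days?** Sometimes. With log-normal days and equal log-scale SDs (so that SD is proportional to the mean), default coverage is 91-98% on the raw scale and 95% after the log. But the log is triggered by non-normality, not by unequal variance. If log-scale spreads differ, the table in step 2 applies to the log scale.

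**4. SAE counts.** The plan gives no rule for zeros, so log(1+count) is used here. Coverage of nominal 95% intervals at 40 v 120, assumed Poisson:

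| Means, HBOT v SOC | Default | HC3 |
|---|---|---|
| 0.2-1.0 v 0 | 71-74% | 94-95% |
| 0.3 v 0.05 | 82% | 94% |
| 0.5 v 0.1 | 85% | 95% |
| 0.5 v 0.2 | 90% | 95% |
| 0.2 v 0.2 | 95% | 94% |
| 0.3-0.5 v 0.8 | 96-98% | 95% |

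Analytic check of the first row, with SOC all zero and HBOT variance s²: the true variance of the difference is s²/40, and the pooled variance is (40s²/160)(1/40 + 1/120) = s²/120. The ratio is 3, so the standard error is understated by √3 = 1.73 and coverage is about 2Φ(1.96/1.73) − 1 = 74%.

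**The case against.** The plan nowhere says that variances are pooled. That is inferred from the default of linear regression and from the single Cohen's d in Section 9.5. This stands, and it is why the point is a missing specification with a known better choice, not a stated error.

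Three stronger readings are tempting, and the documents do not support them.

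- *The listed safety events arise almost only in the chamber, so the SAE interval must be far too narrow.* Sections 4.2.3 and 8.1 do call the four events potentially related to HBOT. But one of them is acute pulmonary edema, which Section 2.3 describes as part of the course of COVID-19. Section 9.2 hypothesises fewer severe adverse effects with HBOT than with SOC. SOC counts could therefore be the higher and more variable, and the default interval would then be too wide. Coverage of 71-74% is the extreme, not the expected case.
- *Robust standard errors would recover power for ventilator days.* With gamma-distributed days, SD equal to the mean, and means of 6 v 10, untransformed data give 45% default v 68% robust power (23 v 96). But such data would trigger the planned log, after which power is 39% v 37% (58% v 58% at 40 v 120). The gain disappears.
- *Results are wrong whenever spreads differ at all.* At SD ratios of 0.9-1.1 size is about 4-6% (40 v 120), which is of little consequence.

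It is also fair that these are a secondary endpoint and a safety summary in a non-randomised pilot.

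**Conclusion.** The concern holds in a limited form. Both regressions and the t-test lack a provision for unequal variances in a design with groups of about 1:3, where the default standard error depends on that assumption. Materially different spreads would take the ventilator-day test from below 1% to 15-18% instead of 5%, and the SAE interval from about 74% in the extreme, through 82-90%, to 96-98% instead of 95%. Neither the size nor the direction can be settled from the documents, because they give no SDs or event rates. The log transformation is a partial safeguard for ventilator days and does not cure the SAE comparison when SOC events are fewer. This is a cheap improvement, worth making before outcomes are compared.

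**What to change.** - **9.4.3 and 9.4.4:** keep the linear regressions, and state that all tests and 95% confidence intervals use heteroscedasticity-consistent (HC3) standard errors. If the matched sets of one HBOT and three SOC patients are modelled, use a variance that is cluster-robust by set.
- **9.4.1:** specify the Welch unequal-variance t-test.
- **Reason to give:** the unequal 1:3 allocation. Do not add a statement that the listed events can occur almost only in the HBOT group, since Section 2.3 speaks against it.

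**Cost.** One sentence in each of three sections; the options are standard in R and SAS, which the plan already names. Intervals become wider when HBOT is the more variable group (about 1.2 to 1.7 times in the SAE scenarios with fewer or no SOC events). With equal variances size is essentially unchanged. HC3 can fall slightly below nominal for rare counts (93% coverage at 0.1 v 0.1), and with strongly skewed raw days the Welch test rejected 6-7%, so the excess is reduced but not fully removed.

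**Not settled by this change.** How zero SAE counts enter a log transformation, and whether ventilator days come from all 160 patients (9.5) or only from those ventilated (4.2.2). Both need their own decision.

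### The log rules in 9.4.3 and 9.4.4 do not deliver the stated comparisons: the log of a zero SAE count is undefined, and a log-scale slope for ventilator days is not a difference in mean days.

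*Combined protocol and SAP*

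**What the plan says.** **Ventilator days.** Section 9.2 hypothesises that "the patients in the HBOT group will spend on average fewer number of days on a ventilator" and sets this against a "null that there is no difference in means between the two groups". Section 9.4.3 has the same aim: "To compare the average number of days spent in ventilator between the two groups, we will use linear regression analysis". The distribution is then checked graphically and "by conducting test for normality". If it departs from normal, "the outcome will be log transformed before proceeding with analysis". Whichever branch is taken, "Slope coefficient along with 95% confidence interval will be reported as an estimate of difference between HBOT and SOC groups". Section 4.2.2 limits this endpoint to patients who were ventilated.

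**SAEs.** Section 9.4.4 counts SAEs per patient and compares the mean count by linear regression. Here the log does not depend on any check: "The outcome will be log transformed to account for the potential violation of normality". The result is to be reported as a difference in means with a 95% interval.

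Section 9.4.1 allows transformations in general but gives no rule for interpreting them. Nowhere does the plan mention an offset for zeros, exponentiating a slope, or a ratio of geometric means. Section 9.1 leaves the formal SAP to the end of a non-blinded study.

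**The concern.** For SAEs, many patients can be expected to have none, and the log of zero does not exist. An analyst who follows the text must either drop those patients or invent an offset after seeing the data. Neither gives the difference in means that the section promises.

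For ventilator days, the quantity estimated depends on a data check. Without the log, the slope is a difference in mean days. With it, the slope is a difference in mean log-days, which is a different quantity under the same label. Durations are usually right-skewed, so the log branch is a realistic outcome. At stake are a named secondary endpoint and the only formal between-group safety comparison. The mortality analysis is not affected.

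**Working it through.** **The plan's own figure.** Section 9.5 gives 80% power for Cohen's d = 0.51 with 160 patients (40 v 120, two-sided 0.05). The normal approximation gives 79.8% and the t-test 79.3%, so the figure reproduces and is not in dispute here. The documents give no mean, SD or distribution for ventilator days and no expected SAE rate. Everything below that needs them rests on stated assumptions.

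**SAE counts.** Assume a Poisson count with mean m per patient, so P(zero) = exp(−m).

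- m = 0.1: exp(−0.1) = 0.905, so about 90% have zero. Dropping them leaves 160 × 0.095 ≈ 15 patients.
- m = 0.5: exp(−0.5) = 0.607, so about 61% have zero. Dropping them leaves 160 × 0.393 ≈ 63 patients.

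An added constant makes the log computable, but the answer then depends on the constant. Going from no SAE to one adds log(2/1) = 0.69 with a constant of 1, and log(1.5/0.5) = log 3 = 1.10 with a constant of 0.5. Neither is a difference in mean counts.

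**Ventilator days: the estimate.** Assume lognormal days with log-SD s, so that mean = exp(μ + s²/2). The log-scale slope is

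μ(HBOT) − μ(SOC) = log(mean HBOT / mean SOC) − (s²(HBOT) − s²(SOC))/2.

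- Equal spread: means of 4 v 5, 8 v 10 and 16 v 20 days all give log(0.80) = −0.223, while the differences are −1, −2 and −4 days. The slope alone does not give the difference in days.
- Equal means, log-SD 1.0 (HBOT) v 0.8 (SOC): slope = −(1.00 − 0.64)/2 = −0.18, although the difference in means is zero.
- Equal means, log-SD 0.6 v 0.8: slope = −(0.36 − 0.64)/2 = +0.14.
- Means 11 v 10, log-SD 1.1 v 0.7: slope = 0.095 − (1.21 − 0.49)/2 = −0.265. The sign is opposite to the difference in means.

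**Ventilator days: the test.** 4,000 simulated trials per row, both groups with a mean of 12 days, days rounded to at least 1, Shapiro-Wilk on the pooled data choosing between a raw and a log t-test. Ventilated patients: 96 SOC (80% of 120) and 32 HBOT (80% of 40). The normality test chose the log in every trial. Nominal rejection is 5%.

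| log-SD SOC v HBOT | Planned procedure | Unequal-variance t-test on days |
|---|---|---|
| 0.8 v 1.0 | about 20% | about 8% |
| 0.8 v 0.6 | about 11% | about 5% |
| 0.8 v 0.8 | about 5% | about 6% |

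With 23 HBOT patients ventilated (57.5% of 40, from the 80% rate and 22.5-point reduction in 9.5), the planned procedure rejects about 18%, 8% and 5%. The day-scale t-test reaches about 10% at worst. A percentile bootstrap on days runs slightly higher than the t-test, at roughly 7% to 13% across these settings.

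**The case against.** A log-scale slope with its interval is a legitimate comparison, normally exponentiated and read as a ratio. Section 9.4.3 calls it a difference and does not say days. Section 9.4.1 also promises raw means and medians. This stands in part: the log analysis is not invalid in itself. But section 9.2 names means, no text asks for a ratio, and raw means by group carry no interval for their difference.

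The inflated rejection rates need unequal log-scale spread, which is assumed. This stands. At equal spread the planned test holds its level for equal means, and only the label of the estimate is wrong. The trigger is also a graph plus a test, and if no departure is found the slope is in days.

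A day-scale analysis is not perfectly calibrated either. This stands too: with skewed data and a small HBOT group it can exceed 5%, and at equal spread it does slightly worse than the planned procedure. Removing the log is therefore one acceptable remedy, not the only one.

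A reader might infer that the log also fails for ventilator days, because never-ventilated patients have zero days and the power statement in 9.5 counts all 160. The documents do not support this. Section 4.2.2 restricts the endpoint to ventilated patients, so those zeros do not enter. The count of 160 is a separate sample-size question.

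For SAEs, a stated offset would make the regression computable. It would still not estimate a difference in means.

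**Conclusion.** Both rules are wrong as written, and the SAE rule is the more serious. Its log is unconditional and undefined for every patient without an SAE, which is 61% to 90% of patients under the assumed Poisson means. The stated analysis cannot be run on the full cohort and would not estimate what it claims to report.

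For ventilator days, the mismatch of scale follows from the text alone: a data check decides what is estimated, and the log branch does not answer the hypothesis in 9.2. The sizes are illustrative. Rejection of about 20% and 11% under equal means holds only for the assumed lognormal data with the unequal spreads shown; at equal spread it is about 5%. It would go too far to say that the test is inflated in general, or that any log-scale result is invalid.

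**What to change.** **Section 9.4.4.** Replace the regression on logged counts. Either compare the proportion of patients with at least one SAE (difference and 95% CI), or model the count by Poisson or negative binomial regression and report a rate ratio with its 95% CI. The proportion is closest to the safety hypothesis in 9.2, which concerns the rate of any severe adverse effect.

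**Section 9.4.3.** Remove the normality check as a switch and fix the scale in advance, in one of two ways:

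1. Keep the hypothesis in 9.2. Report the difference in mean days among ventilated patients from the linear model, with a robust or bootstrap 95% CI. The downside is rejection somewhat above 5% with skewed data and few ventilated HBOT patients (about 5% to 10% for the unequal-variance test above, a little more for the percentile bootstrap).
2. Restate the hypothesis in 9.2 as a ratio of geometric means. Always log the days, and report the exponentiated slope and interval as that ratio.

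The cost is wording only: no new data, patients or visits. The choice should be recorded before outcomes are compared, including at the interim analysis, and not left to a SAP written at the end of the study.
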